3.4 Protocol 3 (Specific Aim 5)

The purpose of this protocol is to validate the readability and usefulness of the CAMCI report with a sample of potential users of the product. We will recruit and test healthcare professionals (N=60) who would be responsible for interpretation of the CAMCI report and decisions concerning patient care (e.g., physicians, physician's assistants, neuropsychologists).

After consent, participants will be presented with a series of case studies including information expected to be available during an assessment of cognitive status (e.g., MoCA, list of medications, patient report, etc.) as well as the results of CAMCI testing, and will be asked to respond to a series of questions related to 1) thoroughness of the information provided, 2) usefulness of information, and 3) recommended course

of action based on the CAMCI report, and 4) their likelihood to use the tool. In addition, the readability of the CAMCI report will be evaluated by requesting the participant to supply information available on the report. Report validation will occur in two phases during Year 1 (N=30) and Year 3 (N=30) in conjunction with the efforts to validate the scoring algorithm and develop the change metric. Each test session will take approximately 60 minutes to complete, and participants will be paid \$100 for completion of this portion of the study.

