Protocol 3: Potential participants will be identified through professional connections, referral, and advertisement. The PI, co-investigators, consultants, and research staff on the project have links to a broad range of academic and clinical departments at Universities and community health care services in the local area and across the country at which we will solicit for professionals interested in participating in the study. In addition, we will research community and health organizations in and around the city of Pittsburgh (spanning a 10 county area) providing varying services to older adults (e.g., rehab facilities, outpatient clinics, physician offices, community centers), and will provide flyers, presentations, and/or additional information to these organizations, as requested, to raise interest in the project and to recruit participants.

- **4.6 Risk/Benefit Ratio.** Some individuals may experience fatigue, frustration, or feel slightly distressed if they think they are not doing well on a test of intellectual ability. If the participant indicates any distress the test will be discontinued, or breaks will be provided, if requested. Other than payment for participation, there are no direct benefits to participants from participating in this study. Participants will be informed that the results of this study may help identify early signs of memory problems. If a previously unknown disorder is identified (i.e., MoCA <10), we will refer the participant to the appropriate health and community services and if consent is provided, the results of the MoCA will be provided to their healthcare provider of choice. Results will not be provided directly to an individual, and as CAMCI is not yet an FDA-cleared tool for clinical assessment, computer test scores collected or reported by the CAMCI will not be released or discussed.
- **4.7 Data and Safety Monitoring Plan.** The PI, Co-Investigators, and DSMB will monitor the study at all stages. Throughout the study, the research personnel will minimally meet monthly to discuss recruitment and conduct of the study. Any instances of adverse events will be reported immediately to the NIA, DSMB, and Copernicus Group IRB using the standard forms and/or procedures that have been established for the clinical trial. The yearly IRB renewal for this study will include a summary report of the Data and Safety Monitoring Plan findings from the prior year.

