- **4.8 Confidentiality.** Participants will be required to sign a Subject Information and Consent form. All information collected for this study will be coded and remain confidential to the extent provided by law. The principal investigator will routinely review the methods of data collection and storage to ensure that no breach of confidentiality occurs. If the results of this study are submitted for publication, confidentiality of records will be maintained. Research records will be kept for a period of at least 5 years after the study ends.
- **4.9 Alternative Treatments.** Not Applicable.
- **4.10 New Information.** Participants will be promptly notified if any new information, either good or bad, develops during the course of this study that may cause a change of mind about continuing to participate.
- **4.11 Costs and Payments.** There are no costs for participating in this study. Participants receive payment for completion of each portion of the study in which they participate (see table below).

| Drot | toco | 1 | ٠. |
|------|------|---|----|
| 10 | | | ٠. |

| •• | | | |
|-------|------------|---------|--|
| Phase | # subjects | Payment | |

| Baseline | 420 | \$100* |
|-----------------------|-----|--------|
| Follow-Up (6 months) | 280 | \$75 |
| Follow-Up (12 months) | 420 | \$75 |
| Follow-Up (24 months) | 140 | \$75 |

^{* \$50} if a valid neuropsychological assessment is available allowing the protocol to be shortened

Protocol 2:

| Phase | # subjects | Payment | |
|----------|------------|---------|--|
| Baseline | 400 | \$100* | |

^{* \$50} if a valid neuropsychological assessment is available allowing the protocol to be shortened

Protocol 3:

| Phase | # subjects | Payment |
|-------------------|------------|---------|
| Report Validation | 60 | \$100 |

4.12 Conflict of Interest. The Principal Investigator, [name], is employed by Psychology Software Tools (PST) and may be perceived to be affected by the outcome of the research study. Therefore, each Subject Information and Consent form discloses this relationship where it is stated "PST employs [name], the principal investigator, who might benefit from commercial use of this product."

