This project is part of a National Institutes of Health Small Business Innovation Research (NIH SBIR) award. SBIR grants are given to profit-making firms in order to develop new products. This grant has been awarded to Psychology Software Tools, of Pittsburgh, which is owned by [name] and [name]. The goal of this project is to commercialize CAMCI as a valid assessment tool for quickly screening cognitive impairment. Some of the data may be reported at scientific conferences or in scientific journals. Drs. [name], [name], and [name] may also benefit from commercialization of this product.

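### Protocol 3 draws some of its clinician raters from the connections of a team with a commercial interest and does not exclude, record or separate raters with ties, so the Aim 5 opinion ratings may be biased upward by an amount the plan cannot detect

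*Protocol*

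**What the plan says.** Protocol section 3.4 plans 60 healthcare professionals, 30 in Year 1 and 30 in Year 3. They read case studies that include CAMCI results. They then judge how thorough and how useful the information is, recommend a course of action, and state "their likelihood to use the tool". Readability is tested separately, by asking them to find facts on the report. No comparison report is described.

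Section 4.5 gives the recruitment routes for Protocol 3: "Potential participants will be identified through professional connections, referral, and advertisement". It adds that "The PI, co-investigators, consultants, and research staff on the project have links to a broad range of academic and clinical departments", and that professionals will be solicited there. It also describes wider outreach: "we will research community and health organizations in and around the city of Pittsburgh", over ten counties, with flyers and presentations.

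Section 4.12 says the principal investigator is employed by the sponsor and is someone "who might benefit from commercial use of this product". It adds that three further doctors "may also benefit from commercialization of this product". The principal investigator's position is disclosed in every consent form.

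The only eligibility criterion specific to Protocol 3 (section 4.3) is to hold a professional post in health care. The only sampling target (section 4.1) is the race, ethnicity and sex mix of the health workforce. The SAP covers validation, agreement and the change metric, and contains no analysis for Protocol 3.

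**The concern.** Three of the Protocol 3 outputs are opinions about a product, and one named way of finding the people who give them runs through a team with a commercial stake in that product. A rater who knows the team may be inclined to be generous, or may already have seen the report. The plan does not make such raters ineligible, does not ask who they are, and does not analyse them apart. Disclosure in the consent form informs the rater but does not change who is sampled.

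At stake is whether a favourable Aim 5 finding can be read as evidence about the report among ordinary users. With no record of ties or route, neither the sponsor nor a later reader could separate the merit of the report from goodwill towards the team.

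**Working it through.** **The plan's own figures.** 30 + 30 = 60, which agrees with the payment table in section 4.11. No alpha, power, precision target, favourable-rating definition or success criterion is given for Protocol 3, so there is no derived figure to reproduce. What follows is for scale only.

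**Where a safeguard could stand.**
- Section 4.3, inclusion: a healthcare post; silent on ties.
- Section 4.4, exclusion: medical, psychiatric, alcohol and MoCA criteria; silent on ties.
- Section 4.5, recruitment: no share or quota per route, and no recording of route.
- Section 4.8, confidentiality: data are coded, but it is not said that investigators cannot see which rater gave which answer.
- Section 4.12, conflict of interest: disclosure in consent forms only.
- SAP: no Protocol 3 analysis, so no sensitivity analysis by tie or route.

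**Bias.** Let *p* be the favourable rate among unconnected raters, *s* the share of raters who are connected, and *d* the extra favourable proportion among them. The expected observed rate is (1 − s)p + s(p + d) = p + s·d, so the bias is s·d. All three values are assumptions. Bias in percentage points:

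| s | d = 5 | d = 10 | d = 20 |
|---|---|---|---|
| 0% | 0 | 0 | 0 |
| 25% | 1.25 | 2.5 | 5 |
| 50% | 2.5 | 5 | 10 |
| 75% | 3.75 | 7.5 | 15 |
| 100% | 5 | 10 | 20 |

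**Sampling error.** The 95% half-width is 1.96·√(p(1 − p)/n). At p = 0.65:
- n = 60: 1.96·√(0.2275/60) = 12.1 points.
- n = 30 (one phase): 1.96·√(0.2275/30) = 17.1 points.

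For p from 50% to 80%, the half-width runs from 12.7 down to 10.1 points at n = 60, and from 17.9 down to 14.3 at n = 30.

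With d = 20 and p = 0.65, the bias passes the n = 60 half-width only when s exceeds 12.1/20, or about 60%.

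**Coverage.** A bias smaller than the half-width still damages the interval. Exact coverage of a nominal 95% Wilson interval at n = 60 and p = 0.60:

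| Bias (points) | Coverage |
|---|---|
| 0 | 95.3% |
| 1.25 | 95.0% |
| 5 | 88.7% |
| 10 | 65.8% |
| 20 | 7.7% |

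**Could the data reveal it afterwards?** Suppose ties were recorded and split the raters 30/30. Power to detect a 20-point difference would be 34.9% (70% v 50%), 39.1% (80% v 60%) or 49.0% (90% v 70%). A subgroup test would not settle the matter, so the protection has to come mainly from who is enrolled and how the ratings are collected.

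**The case against.** A reader might infer that the ratings will be biased upward, that the raters will be the investigators' colleagues, and that everyone whose contacts are used stands to profit. The documents support none of these.

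- **No prediction is possible.** Neither the connected share nor any effect of ties on ratings is given. On the assumptions above, the bias can be negligible.
- **Connections are one route among several.** Section 4.5 also names referral, advertisement and ten-county outreach that includes physician offices and outpatient clinics. The team's links are to departments and services. Someone who answers a solicitation there need not know an investigator or have seen the report.
- **Financial interest is shown for some people only.** It is stated for the principal investigator and three doctors whose roles are not given in that sentence, not for all co-investigators, consultants and staff.
- **Not every output is an opinion of the product.** Fact retrieval and the recommended course of action are not favourability ratings. Fact retrieval in particular is much less open to courtesy.
- **A broad exclusion has a cost.** Section 4.1 treats professional position and expertise in cognitive assessment as the most important qualification. Barring anyone with any past training or collaboration tie could remove well-qualified raters.

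All of these stand, and they limit the wording, the scope and the remedy. None closes the gap: a team with a stated commercial interest is a named source of raters, and the plan collects nothing that would show whether this mattered. Coding the data under section 4.8 does not by itself hide raters from interested investigators.

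**Conclusion.** The point holds as a credible, undetectable risk of upward bias in the thoroughness, usefulness and likelihood-to-use ratings. It does not show that bias will occur. The illustrative size is 0 to 20 points, depending wholly on assumed values of *s* and *d*. At the middle of that range (half of the raters connected, 20 points of inflation) the bias is 10 points, below the 12-point half-width, yet coverage falls to about 66% at a true rate of 60%.

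The issue is confined to Specific Aim 5. The CAMCI accuracy, agreement and change analyses in the SAP are untouched. It should be fixed because the remedy is cheap, while the information cannot be recovered from the data as planned.

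**What to change.** Amend Protocol sections 4.3 and 4.5 for Protocol 3:

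1. Make ineligible anyone with a current employment or financial tie to the sponsor, or a role on the project.
2. Add one screening question that records any other tie to the team, prior exposure to the CAMCI report, and recruitment route. Raters with such ties stay eligible, which keeps the expertise that section 4.1 asks for.
3. Collect ratings so that investigators with a commercial interest do not see who gave them.
4. Keep the advertisement and organisation outreach already described.

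Add a short Protocol 3 paragraph to the SAP. Report the opinion ratings for untied raters alongside the full set, descriptively and with intervals. State in advance what counts as a favourable conclusion, and require it to hold in the untied raters. Do not plan a formal tied-versus-untied test, for which 60 raters give too little power.

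The cost is a short amendment, one extra question, slightly slower recruitment, and a wider interval for the untied subset. If half of the 60 are tied and the favourable rate is 65%, the half-width is about 17 points rather than 12.

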CAMCI: Advancing the Use of Computerized Screening in Healthcare

Clinical Trial:NCT03512301Secondary ID:NIH: 2SB1AG037357-04A1DATE:Approved by DSMB – July 18, 2019
Uploaded to clinicaltrials.gov - February 14, 2025

Analysis Plan

Validation of CAMCI Algorithm and MoCA with Neuropsychological Adjudication

CAMCI will group participants into three classifications: impaired, non-impaired, and intermediate. Likewise, the neuropsychological adjudication will provide a consensus classification for participants into impaired, non-impaired, and intermediate and thus, CAMCI classifications will be compared to clinical adjudication. Similarly, MoCA classification will be evaluated against the neuropsychological adjudication. MoCA scores are classified as non-impaired (MoCA \geq 26) or impaired (MoCA <17), with intermediate scores occurring between 18-25. To validate the CAMCI and MoCA against the neuropsychological adjudication, we will evaluate positive and negative predictive agreement, accuracy and error bias. Accuracy is defined as the correct identification using CAMCI: ACC=[TP+TN]/total; error bias will be a contrast ratio of false positives and false negatives: FP-FN/FP+FN.

Agreement analysis

Two methods will be used to evaluate the agreement of CAMCI to non-reference (Montreal Cognitive Assessment, MoCA) and reference (clinical adjudication) standards. First, using linear regression, agreement analysis will be done to compare the subject device, CAMCI score (expected to range from 0-50), and the MoCA score (ranging from 0-30). Agreement will be evaluated using the scatterplot, linear regression equation and confidence intervals, and Pearson correlation. It will be expected that each of these evaluation methods will show that those patients who score high on the CAMCI will also score high on the MoCA, indicating agreement between the range of scores that are non-impaired. Likewise, we will expect to see low scores on the CAMCI to be found in those who also show low MoCA scores, indicating agreement in the ranges of impaired scores on both assessments.

Next, agreement will be assessed using the clinical adjudication categories and the CAMCI classifications. The following table will be used to display the frequencies showing the distribution of patients into the CAMCI classifications (impaired, non-impaired, intermediate/indeterminate) by clinical adjudication (normal, impaired, indeterminate). From this summary, percent agreement (positive and negative), confidence interval estimates, and quadratic weighted kappa will be used to assess the agreement between CAMCI and the reference standard. Finally, this analysis will be repeated with the omission of the intermediate group to show the performance of CAMCI for those who are clearly impaired and clearly non-impaired.

Classification						
TEST		Impaired	Intermediate	Non-impaired		
	Impaired	TP*	FP	FP		
	Intermediate	FN	TP	FP		
	Non-impaired	FN	FN	TN		

Example, Agreement analysis (general case in 3x3):

* TP=True Positive, TN=True Negative, FP=False Positive, FN=False Negative

Example, Agreement analysis (for current study):

Classification by Clinical Adjudication							
CAMCI		Impaired	Intermediate	Non-impaired			
	Impaired	а	b	С			
	Intermediate	d	е	f			
	Non-impaired	g	h	i			

Classification by Clinical Adjudication							
МоСА		Impaired	Intermediate	Non-impaired			
	Impaired	а	b	С			
	Intermediate	d	е	f			
	Non-impaired	g	h	i			

Positive percent agreement (PPA, %) = 100 X (a + e) / (a + b + c + e + f) Negative percent agreement (NPA, %) = 100 X (i) / (d + g + h + i) Accuracy (ACC) = [(a + e) + (i)] / total n Error Symmetry ([(b + c + f) – (d + g + h)] / total n

Change Metric

Test-retest descriptive statistics (mean, standard deviation) will be calculated and compared for the clinical groups (impaired, intermediate, non-impaired). Difference scores will be calculated and analyzed for retest effect and to identify any patterns (improvement/decline) that might differ between the groups on retest. Finally, repeated measures analyses will be used to assess group X retest differences. This information will be used to determine whether adjustments will be made to the reliable change calculations.

Change in test scores will be modelled using a Reliable Change Index (RCI) method to determine whether the change in test scores is due to the reliability of the measure (rather than due to chance alone). This method is beneficial because it is well-documented and is one that accounts for measurement error and practice effect (Chelune et al., 1993; Hensel, 2007). It has also been shown (Hsu et al., 1999) to account for regression to the mean. Reliable change will be evaluated at the 6-month, one-year, and two-year intervals.

Using normative data from a prior sample, and data gathered from the non-impaired clinical group, an appropriate strategy will be identified for the identification of cut-off scores for clinically significant change (Jacobson and Truax, 1991). Data will then be used to derive standard error of the mean (SEm), test-retest reliability coefficients, and standard error of the difference (SEdiff) statistics. The latter, SEdiff, will identify the variability in the distribution of the change scores that would be expected if there were no change between test and retest. Finally, 90% and 95% confidence intervals will be calculated to identify the amount of difference that would have to be observed in either direction to assume that the difference occurred beyond chance (at significance levels of 5% and 2.5%, respectively).

Reliable change will be calculated using the following formula for all data regardless of clinical group:

$$RC = \frac{x_2 - x_1}{SE_{diff}}$$

Using established methods (Chelune et al. 1993), index scores will classify patterns of change as "gain", "no change", and "loss". Likewise, the same individuals will be grouped based on change in clinical adjudication between those identified as impaired, intermediate, and non-impaired at each assessment, categorizing status change as "improved", "no change", and "declined". These groups will be analyzed based on the confidence intervals, accuracy, and reliable change index. Analysis will include the assessment of practice effect.

References

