- **4.2. Inclusion of Children in Research.** This study deals with disorders of memory in adults associated with aging and other causes. Therefore, the study is not applicable to children.
- **4.3 General Inclusion criteria.** Signed informed consent; adequate visual and auditory acuity to allow neuropsychological testing; able to read, write and understand study and test requirements; within the age range of 60+ (Protocols 1 and 2), professional position in a healthcare field (Protocol 3).
- **4.4 General Exclusion criteria.** Any significant neurologic disease, such as multi-infarct dementia, Parkinson's disease, epilepsy, stroke, multiple sclerosis or head trauma; history of major depression or other major psychiatric disorder, such as, schizophrenia and bipolar disorder; history of consuming 5 or more alcoholic drinks per day on a regular basis; MoCA score <10.

4.5 Recruitment Procedures.

Protocols 1-2: Potential participants will be identified by a subject recruiter through response to advertisement or referral, and at a variety of community and clinical sources (e.g., PCP offices, local churches, community centers, clinics). The test is purely cognitive, so no medical records will be requested. The subject recruiter will describe the study to the participant and ask if they are interested in participating. If they express an interest, study staff will meet with the participant to discuss the study in detail and to obtain informed consent. Participants who fail to demonstrate an adequate understanding of the material reviewed during the informed consent process, or who score <10 on the MoCA will be excluded.

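### A MoCA score of 17 falls in none of the SAP's three bands, so eligible participants with that score have no row in the MoCA-versus-adjudication table

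*SAP*

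**What the plan says.** The SAP, under Validation of CAMCI Algorithm and MoCA with Neuropsychological Adjudication, sets three MoCA classes. Non-impaired is a score of at least 26. The other two are "impaired (MoCA <17), with intermediate scores occurring between 18-25".

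The classes feed a planned analysis: "To validate the CAMCI and MoCA against the neuropsychological adjudication, we will evaluate positive and negative predictive agreement, accuracy and error bias". Under Agreement analysis, the SAP prints a 3x3 table of MoCA class by adjudicated class with rows impaired, intermediate and non-impaired only. The formulas below it include "Accuracy (ACC) = [(a + e) + (i)] / total n", and error symmetry is also divided by the total.

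On eligibility, Protocol section 4.4 lists "MoCA score <10" as the only MoCA-based exclusion. No other part of either document gives a different MoCA cut-off or a rule for a score of 17.

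**The concern.** The two lower cut-offs do not meet. A participant scoring 17 can be enrolled, tested and adjudicated, yet has no MoCA class. The analyst then has two options, and the SAP supports neither.

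- **Drop the 17s.** MoCA and CAMCI are then judged against adjudication on different sets of participants.
- **Assign them.** The boundary between impaired and intermediate is then chosen by a rule not written in advance, possibly with results in view. The choice has a direction. Moving a 17 from impaired to intermediate turns a true positive into a false negative if adjudication says impaired, and a false positive into a true positive if adjudication says intermediate.

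The reported performance of the comparator can therefore go up or down with an unwritten decision. Protocol section 4.12 discloses a commercial interest in CAMCI. That implies no misuse, but it is a reason to settle the comparator's cut-offs beforehand.

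**Working it through.** **1. Is there a gap?** Inputs are the three SAP bands and the eligible range 10-30 (Protocol 4.4; the SAP gives the full scale as 0-30). Checking each whole number:

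| Eligible scores | Class | Number of values |
|---|---|---|
| 10-16 | impaired | 7 |
| 17 | none | 1 |
| 18-25 | intermediate | 8 |
| 26-30 | non-impaired | 5 |

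The total is 7 + 1 + 8 + 5 = 21 values. Only 17 is unplaced, and no score is in two bands. If the intermediate range were read as excluding its end points, 18 and 25 would be unplaced as well, so 17 is unplaced on either reading.

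**2. What does the choice move?** Label the SAP's cells a, b, c (impaired row), d, e, f (intermediate row) and g, h, i (non-impaired row). The columns are adjudicated impaired, intermediate and non-impaired. Let x, y and z be the numbers scoring 17 who are adjudicated to each column in turn. Calling 17 intermediate rather than impaired moves x from a to d, y from b to e, and z from c to f. From the SAP's formulas:

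- Accuracy, (a+e+i)/n, changes by (y - x)/n.
- Error symmetry, [(b+c+f) - (d+g+h)]/n, changes by -(x + y)/n.
- PPA, (a+e)/(a+b+c+e+f): the numerator changes by y - x and the denominator by -x.
- NPA, i/(d+g+h+i): the denominator rises by x.
- z cancels in all four, because c and f are both counted as false positives. Those participants matter only if 17s are dropped.

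**3. How many people?** The documents give no MoCA distribution. *Assumption:* a normal distribution discretised and truncated to 10-30, mean 21-25, SD 3-5, applied to the 420 of Protocol 1.

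| Assumed mean, SD | Share scoring 17 | Expected of 420 |
|---|---|---|
| 25, 3 (lowest) | 0.4% | 1.7 |
| 24, 4 | 2.3% | 9.6 |
| 21, 4 (highest) | 6.1% | 25.7 |

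Each person moves accuracy or error symmetry by at most 1/420 = 0.24 points. Ten people move either by at most 10/420 = 2.4 points, and the cap over the whole range is 0.4 to 6.1 points. This cap does not apply to PPA or NPA, which have smaller denominators.

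**4. Illustration.** *Assumed* table without the 17s (n = 410), with columns in the order above: impaired row 9/3/1, intermediate row 39/118/106, non-impaired row 4/23/107. Ten people scoring 17 are added (n = 420). Each cell shows 17 called impaired, then 17 called intermediate.

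| Adjudication of the ten (x/y/z) | PPA % | NPA % | Accuracy % | Error symmetry |
|---|---|---|---|---|
| 10/0/0 | 55.5 → 53.6 | 61.8 → 58.5 | 58.1 → 55.7 | 0.105 → 0.081 |
| 0/10/0 | 51.4 → 55.5 | 61.8 → 61.8 | 55.7 → 58.1 | 0.129 → 0.105 |
| 5/4/1 | 53.4 → 54.1 | 61.8 → 60.1 | 56.9 → 56.7 | 0.117 → 0.095 |
| 0/0/10 | 51.4 → 51.4 | 61.8 → 61.8 | 55.7 → 55.7 | 0.129 → 0.129 |

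First row worked through: PPA is (19+118)/(19+3+1+118+106) = 137/247, becoming 127/237. NPA is 107/173, becoming 107/183. Accuracy is 244/420, becoming 234/420. Error symmetry is (110-66)/420, becoming (110-76)/420.

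In the last row the two assignments agree, but dropping the ten gives PPA 127/237 = 53.6% instead of 51.4%, and accuracy 234/410 = 57.1% instead of 55.7%.

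The SAP text also defines error bias as a contrast of false positives and false negatives. Read as (FP-FN)/(FP+FN), it goes from 44/176 = 0.250 to 34/186 = 0.183 in the first row.

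**The case against.** The gap itself is hard to dispute, so the best case against is about weight.

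- **Little depends on it.** CAMCI is the device under study and MoCA is a non-reference comparator. No hypothesis, success threshold or test of CAMCI accuracy against MoCA accuracy is attached to the MoCA table, so no planned conclusion can flip. This stands, and it limits the reach of the point. The table is nonetheless a planned result that cannot be reproduced from its own SAP.
- **A 17 can only be impaired or intermediate.** True, since the bands are ordered and the gap is one integer wide. One could read intermediate as whatever lies between the two named classes, but the printed lower limit of 18 contradicts that. Choosing between the two classes is exactly what the SAP leaves open.
- **The size rests on assumed inputs.** This stands. In the mixed 5/4/1 case accuracy moves only 0.2 points and PPA 0.7, because the x and y effects partly cancel; NPA moves 1.7 points and error symmetry about 0.02. The larger movements need all the 17s to be adjudicated alike.
- **The denominator may not be 420.** The SAP does not say whether the 400 participants of Protocol 2 are pooled. If they are, each person counts for 1/820 = 0.12 points, but there would also be more people scoring 17.
- **A symbol may have been lost in reading the PDF.** This is possible but unlikely, because the at-least sign in the same sentence came through.

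**Conclusion.** The concern holds. As printed, 17 is the one eligible MoCA score with no class, and the planned MoCA-versus-adjudication table cannot be completed without a rule the SAP does not give. That conclusion rests on the documents alone.

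The size is probably modest and depends on assumptions: about 2 to 26 of 420 people under the assumed distributions, and at most 0.24 points each on accuracy or error symmetry. PPA and NPA can move somewhat more (about 4 points and 3 points for ten people in the extreme illustrated cases). These counts are upper bounds on those whose assignment matters, since 17s adjudicated non-impaired change nothing unless they are dropped.

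The scope is the MoCA table only. The CAMCI-versus-adjudication table is untouched, as is its kappa, which the SAP specifies for CAMCI ("quadratic weighted kappa will be used to assess the agreement between CAMCI and the reference standard"). So are the CAMCI-MoCA regression and correlation, which use the raw score, and the change metric, which groups by adjudication. The point should be corrected, but it does not threaten the main CAMCI validation.

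**What to change.** Before analysis, reconcile the two printed cut-offs according to the one the sponsor intended. Either impaired becomes 17 or below with intermediate 18-25, or impaired stays below 17 with intermediate 17-25. Each version places every score from 0 to 30 in exactly one class; the eligible values split 8/8/5 or 7/9/5 (impaired/intermediate/non-impaired). The documents do not show which was meant, so the sponsor must decide, and the chosen rule should then apply throughout.

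If the analysis has already been run, state how scores of 17 were classified or whether they were dropped, how many there were, and give the MoCA PPA, NPA, accuracy and error symmetry under both assignments.

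The cost is a one-character change to the SAP, or one extra run of the MoCA table. No new data are needed.
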